At 6 weeks, 3 months and 6 months postop, all Veterans will receive REDCap automated survey invitations and, if they have consented to participate in the Department of Veterans Affairs' Annie mobile Short Message Service (SMS) text messaging, short text messages reminding them to take the survey. If participants prefer, paper copies of these surveys will be mailed to them with a cover letter. At 6 weeks, the survey will include: BPI; DASS-21; PCS; OQ-45.2; KOOS - postop; CPAQ; CPVI; Promise Sleep; Complications; and workshop usefulness (6wk). At 3 months, the survey will include: BPI; DASS-21; PCS; PMSS (postop); OQ-45.2; KOOS - postop; CPAQ; CPVI; and Promise Sleep. At 6 months, the survey will include: BPI; DASS-21; PCS; PMSS (postop); OQ-45.2; KOO - postop; CPAQ; CPVI; Promise Sleep; Workshop Usefulness (6mo); and COVID-19 Impact.

Survey Review

In each case, after the participant has completed the surveys, the RAs will cross-check the medications reported in the BPI and DASS-21 with those in the medical record and discuss discrepancies with the participant.

Data Collection and Quality Assurance

Data management

The Study Coordinator at the Coordinating Site will be responsible for:

1. Designing and maintaining the REDCap data collection site as well as the Tracking Database
2. Ensure all data is stored so that blinded study personnel do not have access to any data that would un-blind them.
3. Conduct regularly scheduled audits (including hard-copy-to-electronic-copy checks) and data quality checks

REDCap

All data collection forms will be available through a REDCap (Research Electronic Data Capture) database (supported by the institutional CTSA) and patients can directly enter data into these forms. They will enter data into a central database through their computer or a tablet provided in the clinic. This will eliminate error in data entry, and reduce time necessary for data entry, cleaning and analysis. Range checks will be programmed into the data entry system when the nature of the data allows so that it will not permit invalid values to be entered into the database.

When a data collection session is completed, the RA will review electronic forms for completeness and validity. The RA will resolve all queries and will enter an override for all values that have been confirmed as being accurate. Reports will also be run periodically to confirm or correct questionable values. All changes will be tracked through the REDCap audit trail.

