3. Review interim data in the context of the most recent scientific literature and access unmasked data if necessary.
4. Ensure that the study does not continue beyond the point when objectives have been met and a clinically meaningful answer of importance to the scientific community and the public has been obtained.

Responsibilities of the SMC

1. Approve study protocols and plan for data and safety monitoring.
2. Establish and approve reporting guidelines for unanticipated events.
3. Review unanticipated events and make recommendations as appropriate to needed changes in research protocols, the informed consent process/document or other corrective actions in order to protect the safety, welfare, or rights of subjects or others.
4. Review recruitment and retention data.
5. Review interim analysis of outcome data for early evidence of efficacy, lack of efficacy, or evidence of study futility.
6. Review published reports of related studies submitted by the study investigators, or SMC members to determine whether the monitored study needs to be changed or terminated.
7. Review the proposed stopping guidelines as specified in the protocol and, at its discretion, recommend modification to the proposed plan, or propose a plan, if none has been proposed.

Meetings of the SMC

The focus of the **open** session of each meeting is on the general conduct and progress of the study. Specifically, the focus of the open session is: unanticipated events, subject accrual, protocol compliance, site performance, quality control, and timeliness and completeness of follow-up. During this time, no confidential data will be discussed and the blind will be maintained. The PI and other appropriate study leadership and the protocol specific biostatistician should be in attendance in order to present results and respond to questions.

The focus of the **closed** session of each meeting will be on grouped safety data and, if appropriate, efficacy data to include unmasking of blinded data presented by the protocol specific statistician(s).

Recommendations will be made to continue the study as planned, to make adjustments to the study plan, suspend or to terminate the study during the **executive** session, attended only by the SMC members.

The co-PIs will:

1. Schedule the meetings of the SMC and draft the agendas (to be approved by the SMC).
2. Ensure meeting materials are distributed to each SMC member prior to meetings and in sufficient time to permit adequate review.

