Upon enrollment, all participants will be provided with the phone number of the local VAMC's Suicide Prevention Coordinator as well as the Veteran crisis hotline. If at any time during participation in study assessments, the workshop or "booster" session a participant indicates suicidal ideation, a research team member will ask 3 follow-up questions as indicated by the Suicide Risk Protocol. If these follow up questions suggest that suicide is imminent (i.e., the participant answers 'yes' or 'maybe' to question 3 of the Suicide Risk Assessment or describes a detailed plan to kill him/herself on a specific date in the immediate future), emergency services will be utilized as per the protocol detailed in the "Suicide Risk Management" document. In addition, patients with imminent risk of suicide, attempts of suicide, incidents of violence toward others, or psychiatric hospitalizations will lead to withdrawal from the research protocol and will be reported to the SMC, institutional IRB and NINR.

Protecting Confidentiality of Participant Data

A number of precautions will be undertaken in order to protect the confidentiality of study participants. All documents containing identifying information (e.g. consent forms, patient correspondence) will be kept separate from the participant's main data file at each site. The main data file will contain only study identifier numbers. A separate key that links the two sets of files will be kept by the study coordinator in a separate locked file. All data will be locked in the research offices of the PIs and study site coordinators. The PIs will have a shared electronic folder in order to share information. Only the PIs and key research staff will have access to this electronic folder. The computers on which data are entered will also be kept in the locked research offices; access to the computers is password-protected. Computer data will be entered by subject code only (without identifying information). The codes will be kept in a locked safe or a password-protected database, in an encrypted computer behind the VA firewall. No subject will be identified by name in any report of the study. Data will be kept confidential and will not be released to the general public. Data will be available to research staff, institutional IRB's and government agencies as required.

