To protect participant confidentiality in the small-group discussions, participants will be reminded at the beginning of small-group discussions not to bring up personal information that they would not want disclosed to others, and they will be asked not to discuss details of the group discussion with anyone outside the group. During small-group discussions, the facilitator will be mindful of potential breaches of confidentiality or personal revelations that might prove harmful, remind participants of the confidentiality rules and stop discussions if appropriate.

Procedures for Identifying, Reviewing, and Reporting Unanticipated Events

An unanticipated problem involving risks to subjects or others is any event or problem that:

- 1) was unexpected (in terms of nature, severity or frequency) given the research procedures that are described in the protocol-related documents, such as the IRB- approved research protocol and informed consent document and the characteristics of the subject population being studied; AND
- 2) was related or possibly related to participation in the research (possibly related means

there is a reasonable possibility that the incident, experience or outcome may have been caused by the procedures involved in the research); AND

3) suggests that the research places subjects or others (those not directly involved in the research such as research staff or family members) at a greater risk of harm (including physical, psychological, economic, or social harm) than was previously known or recognized.

Examples of unanticipated events involving risks to subjects or others include, but are not limited to:

- 1) a breach of confidentiality
- 2) a subject complaint when the complaint indicates unexpected risks or cannot be resolved by the investigators,
- 3) a research team member experiences harm in the conduct of the study,
- 4) a new risk of the study procedure is identified by an outside source (sponsor, federal regulatory agency, outside site, etc.)

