All unanticipated events shall be reported to the co-PIs and both site directors, the SMC, institutional IRBs and NINR within 5 working days of their occurrence. They will also be recorded in a shared database which will be reviewed at the monthly meetings of the Steering Committee and yearly meetings of the SMC. A summary of recommendations made by the SMC in response to any unanticipated event, as well as notice of any actions taken by the IRB regarding the research and any responses to those actions, shall also be reported to NINR within 5 working days.

Compliance across Sites

Procedures to ensure compliance with the monitoring plan and reporting requirements across sites include:

1. All meetings of the SMC shall also be attended by the co-PIs and project directors at each site and the project biostatistician ([name]).
2. All communications from the SMC shall be sent to the co-PIs and project directors at each site.
3. The reporting procedure for unanticipated events shall be documented in a common Manual of Operations.
4. Changes to study procedures proposed and approved by the SMC shall be announced at the monthly Steering Committee meetings and the common Manual of Operations updated accordingly.
5. All screening, outcome, and unanticipated event data shall be stored in common databases. All data requested by the SMC or NINR shall be compiled from these databases by the senior project coordinator, reviewed by the project coordinator at the other site/s, and approved by the co-PIs.

Assessment of External Factors or Relevant Information

Published reports of related studies will be monitored by the study investigators or SMC members through PubMed searches and attendance at scientific meetings prior to SMC meetings. These reports

will be submitted for review prior to annual SMC meetings, or as needed, to determine whether the monitored study needs to be changed or terminated.

Interim Analyses

An interim analysis of outcome data for early evidence of efficacy, lack of efficacy, or evidence of study futility will be performed at the discretion of the SMC. These data will be reviewed at the SMC closed meeting, as appropriate.

Study Completion and Closeout Procedures

Study closeout activities are performed to confirm that the site investigator's study obligations have been met and post-study obligations are understood.

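### The safety log and its 5-working-day report take only events already judged unexpected, related and risk-raising, so several kinds of harm have no planned count by arm and the named psychiatric events have no stated reporting time

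*Combined protocol and SAP*

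**What the plan says.** All references are to the combined protocol and SAP.

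- **Procedures for Identifying, Reviewing, and Reporting Unanticipated Events.** Three tests are joined by AND. The event "was unexpected (in terms of nature, severity or frequency) given the research procedures that are described in the protocol-related documents"; it "was related or possibly related to participation in the research"; and it suggests that the research places people "at a greater risk of harm (including physical, psychological, economic, or social harm) than was previously known or recognized". Events that qualify go to the co-PIs, site directors, SMC, "institutional IRBs and NINR within 5 working days of their occurrence. They will also be recorded in a shared database", which the Steering Committee reviews monthly and the SMC yearly.
- **Minimizing Risk Associated with Suicidal Ideation and Psychological Distress.** Imminent suicide risk, suicide attempts, violence toward others and "psychiatric hospitalizations will lead to withdrawal from the research protocol and will be reported to the SMC, institutional IRB and NINR". No time limit is given, and the section does not say whether these count as unanticipated events.
- **Meetings of the SMC.** The closed session "will be on grouped safety data and, if appropriate, efficacy data", with unmasking possible. The content of the safety data is not defined.
- **6 Weeks, 3 Months and 6 Months Post-Op Surveys.** The 6-week list ends "Promise Sleep; Complications; and workshop usefulness (6wk"). The 3- and 6-month lists have no Complications form. DASS-21 and OQ-45.2 are collected at all three.
- **Data Analysis.** Reasons for drop-out are compared between arms. Perioperative variables, including postoperative complications, are checked for group differences when covariates are chosen.
- **Blinding.** Project coordinators and workshop facilitators are not blinded.

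**The concern.** Whether distress or a hospital admission was caused by a one-day group workshop can rarely be settled from a single case. The more reliable evidence is a comparison of event counts between randomized arms, and that needs events recorded before anyone decides on cause. Here the decision comes first and acts as an entry test for the log.

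The population makes this more than a formality. Veterans can qualify partly on anxiety, depression, stress or catastrophizing scores, and the protocol itself plans for suicidal ideation. At stake are the SMC's view of harms during the trial and the basis for reporting event-level harms by arm at the end.

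Two timing questions follow. A confidentiality breach, listed outright as an example, has a 5-working-day report, while a suicide attempt has no stated deadline unless it also passes the three tests. And a clock that starts at occurrence can run out before the team has heard of the event.

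**Working it through.** The documents give no event rate and no safety sample size, so there is no figure to reproduce. The check sets the sections side by side.

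**1. What the filter does to a comparison.** For arm *a* let N be the number of participants, r the true event rate and c the share of events that pass all three tests. The expected logged count is N × r × c. With equal N, the ratio of logged counts is

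(r_ACT / r_AC) × (c_ACT / c_AC).

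The log estimates the rate ratio only if c_ACT = c_AC, and nothing in the plan secures that. The documents do not say who applies the tests, and some staff know the arm. Distress after a therapy workshop may also be judged related, or expected, more or less readily than distress after an education workshop. Purely to illustrate, with assumed shares:

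- Equal true rates, c = 0.50 versus 0.25: the log shows 1 × (0.50/0.25) = 2.
- A true ratio of 2, c = 0.25 versus 0.50: the log shows 2 × (0.25/0.50) = 1.

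**2. The frequency limb.** An unusual frequency of a known event can satisfy test 1. To see it, someone must count the known events. A typical known event fails test 1 on nature and severity, so it is not logged, and no other tally is named. The limb has nothing to work from.

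**3. Which harms have another route?**

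| Harm | Route outside the log | By-arm comparison planned? |
|---|---|---|
| Imminent suicide risk, attempts, violence, psychiatric hospitalization | Reported to SMC, IRB and NINR without the three tests; withdrawal | Indirectly, through drop-out reasons |
| Anxiety and depressive symptoms | DASS-21 at 6 weeks, 3 and 6 months | Yes, as mean scores |
| Complications to 6 weeks | Complications form | Yes, in the covariate check |
| Complications after 6 weeks | None named | No |
| Suicide Risk Protocol activations, not imminent | None named | No |
| Non-psychiatric hospitalizations | None named | No |
| Deaths | Only as a possible drop-out reason | No safety count |

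The last four rows are the gap. Locations of data by type lists no adverse-event record. Compliance across Sites names screening, outcome and unanticipated-event data as the databases from which SMC requests are met, and no other safety category.

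**4. Length of the complications gap.** Six months is about 26 weeks. 26 − 6 = 20 weeks, or 20/26 = 77% of postoperative follow-up, comes after the only Complications form. Before surgery, the Termination section allows about one year from workshop to operation, and no survey is scheduled in that interval.

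**5. The clock.** The 3- and 6-month surveys are about 13 weeks apart. An event at home soon after the 3-month survey could first be learned of up to about 13 weeks later, against a limit of 5 working days (one week) from occurrence. Staff must tell the site PI immediately once they become aware, but that does not move the start of the clock.

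**The case against.** The strongest reply is that the log is only one of several safety channels. The named psychiatric events reach the SMC with no test of expectedness or relatedness. Drop-out reasons, early complications and distress scores are all compared by arm. A confidentiality breach, a risk of the group format, is expressly loggable. The SMC may see unmasked data, request data from common databases and set reporting guidelines. A death would presumably surface among drop-out reasons. The Manual of Operations and the Suicide Risk Management document are cited but not supplied, and either may hold a deadline or an event log.

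Most of this stands, and it rules out several stronger readings that a reader might infer:

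- *That an arm imbalance in the trial's named risks cannot be seen, that the SMC cannot do its job, or that harms cannot be reported by arm.* The routes above contradict all three. The closed-session data are undefined, which is a weaker criticism than absent.
- *That the psychiatric events lie outside the 5-day rule.* No section classes them as anticipated, and the listed examples of unanticipated events are not exhaustive. One that met all three tests would be under the clock. The supportable point is that the two sections are not reconciled.
- *That such an event could wait a year for the SMC.* The report to the SMC is not tied to the annual meeting.

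The reply does not close the gap. The drop-out comparison is an analysis step that is not named as SMC input. Distress scores are group means, not event counts. The complications check uses information from a form that stops at 6 weeks.

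**Conclusion.** The point holds in limited form. A log filtered by expectedness, relatedness and risk cannot support an unbiased comparison between arms, and four kinds of event have no planned safety count by arm: deaths, non-psychiatric hospitalizations, non-imminent Suicide Risk Protocol activations, and complications after the 6-week survey. The reporting time for the named psychiatric events is unstated, and the 5-day clock can expire before the team is aware.

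The numerical size is unknown. If event rates were between 1% and 6% (an assumption), 215 per arm would give 215 × 0.01 = 2 to 215 × 0.06 = 13 events per arm. A by-arm table would therefore be mainly descriptive, and workshop clustering would reduce its precision further. Its value is that the counts exist and are not pre-selected.

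The conclusion assumes that the documents not supplied do not already provide these counts or a deadline. If they do, the protocol should say so. The efficacy analyses are unaffected. This is a cheap improvement, not a flaw that threatens the trial's main result.

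**What to change.** 1. Record every death, hospitalization, suicide attempt, Suicide Risk Protocol activation and complication from the workshop to 6 months, regardless of expectedness or relatedness. Judge those afterwards, as separate fields. Give the SMC the counts by arm in closed session, and say that this table is part of the grouped safety data.
2. Add the existing Complications form to the 3- and 6-month surveys.
3. Reconcile the section on suicidal ideation and distress with the section on unanticipated events: state whether the named psychiatric events are unanticipated events and the time within which they are reported. Run the reporting clock from when the study team becomes aware.

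The cost is one REDCap event form, one table per SMC meeting, and a few more minutes for participants and research assistants at two surveys. No endpoint, sample size or treatment procedure changes.
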